6.1.10. Visit 10 (End of Stage 1) Telephone Contact

Only when the randomization codes have been released by the sponsor/designee to the investigator may Visit 10 occur. The procedures and order to be followed at the Visit 10 telephone contact are as follows:

Upon receipt of randomization codes from sponsor, contact the subject's parent(s)/legal guardian and perform the following:

- Record nonstudy vaccinations.
- Complete the source documents and CRFs.
- Notify the parent(s)/legal guardian of the child's randomization group, and manage as follows:
 - Bivalent rLP2086-vaccinated subjects (sentinel- and expanded-enrollment cohorts, irrespective of dose level) who completed Stage 1 are eligible to progress to Stage 2 (Section 6.2). Schedule an appointment for the next clinic visit in approximately 12 months (24 months [±1 month] after Visit 6).
 - All subjects randomly assigned to HAV vaccine who complete Stage 1 will finish the study requirements with this contact.

6.1.11. Discontinued Sentinel Subjects/Cohorts

For any sentinel subject/cohort that is discontinued from the study on IRC/EDMC recommendations, the following procedures will be performed at Visit 4 or within 2 weeks after receiving notification of discontinuance if Visit 4 has been attended:

- Perform a brief physical examination comprising general appearance, ears, throat, heart, and lungs. Measure heart rate, respiratory rate, and temperature.
- Record nonstudy vaccinations.
- Where applicable, review the subject's e-diary data and follow up on any ongoing reactogenicity or use of antipyretic medication.
- Collect the e-diary.
- Using the study visit AE checklist as a guide:
 - Inquire whether the subject had any NDCMCs since the last visit. Inquire whether the subject had any of the following related to the AE since the last visit:

hospitalizations, visits to other medical facilities and medication use. Please refer to the SRM for additional details.

- Inquire about neuroinflammatory and autoimmune conditions, such as transverse myelitis, uveitis, optic neuritis, and multiple sclerosis. Refer to the SRM for additional details.
- ➤ Record AEs as described in the AE reporting section (Section 8.14) and the Schedule of Activities. The time of onset will be recorded for any AE that occurred on the same day as investigational product administration.
- Review AEs that were ongoing from the previous visit and record their end dates or confirm that they are still ongoing.
- Record any AE-related hospitalizations or visits to medical facilities or healthcare practitioners. See SRM for additional details.
- Record concomitant medications used to treat AEs (see Section 5.7 and Section 7.6.4).
- Ask the subject's parent(s)/legal guardian to contact the investigator immediately if any significant illness or hospitalization occurs.
- Notify the subject's parent(s)/legal guardian that a telephone contact (Section 6.1.10) will occur approximately 6 months following the last study vaccination for safety follow-up.
- Complete the source documents.
- Complete the CRFs.

6.1.12. Subjects Who Withdraw Prior to Visit 8

For those subjects who withdraw before Visit 8, a telephone contact will occur approximately 6 months after the subject's last study vaccination:

- Using the study visit AE checklist as a guide:
 - ➤ Inquire whether the subject had any NDCMCs since the last visit. Inquire whether the subject had any of the following related to an AE since the last visit: hospitalizations, visits to other medical facilities, and medication use. Please refer to the SRM for additional details.
 - Inquire about neuroinflammatory conditions and autoimmune conditions, such as transverse myelitis, uveitis, optic neuritis, and multiple sclerosis. Please refer to the SRM for additional details.

- Record AEs as described in the AE reporting section (Section 8) and the Schedule of Activities. The time of onset will be recorded for any AE that occurred on the same day as investigational product administration.
- Review AEs that were ongoing from the previous visit and record their end dates or confirm that they are still ongoing.
- Record any AE-related hospitalizations or visits to medical facilities or health care practitioners. Refer to the SRM for additional details.
- Record concomitant medications used to treat AEs (see Section 5.7 and Section 7.6.4).
- Record nonstudy vaccinations.
- Complete the source documents and CRFs.
- Notify the parent(s)/legal guardian of the child's randomization group and manage as follows:
 - Bivalent rLP2086-vaccinated subjects will complete the study requirements with this contact
 - Subjects randomly assigned to receive HAV vaccine/saline will complete the study requirements with this contact.
 - Parent(s)/legal guardian of any subject randomly assigned to the HAV vaccine/saline cohort who did not complete Stage 1 should be informed to make arrangements to have the subject receive a booster vaccination of HAV vaccine using commercially available product.

6.2. Stage 2

Visit 11 should only be conducted for subjects who were randomly assigned and received 3 doses of bivalent rLP2086 at either dose level (60 µg or 120 µg).

6.2.1. Visit 11, Study Month 30, Immunogenicity 1 (24 Months After Vaccination 3 ± 30 Days)

- Confirm that the subject continues to be eligible for the study and does not meet any withdrawal criteria (Section 6.4).
- Confirm that the subject has not received a dose of systemic antibiotics less than 5 days before blood collection (Section 4.4). If the subject has received such a dose, delay the visit to meet the 5-day exclusionary period.

Final Protocol Amendment 2, 19 April 2016

- Confirm that the subject has not received blood products or immunoglobulin within the last 6 months. If the subject has received such products, discuss delaying the visit with the sponsor.
- Obtain a 5-mL blood sample. Local anesthetic may be applied prior to the blood draw.
- Record any AEs and RRIs occurring within 48 hours after the Visit 11 blood draw as described in Section 8 and the Schedule of Activities.
- Record nonstudy vaccinations received since the last study visit.
- Issue a memory aid.
- Schedule an appointment for the next study visit and confirm that it is scheduled within the time window per protocol.
- Complete the source documents and CRFs.

6.2.2. Visit 12, Study Month 42, Immunogenicity 2 (36 Months After Vaccination 3 ± 30 Days)

- Confirm that the subject continues to be eligible for the study and does not meet any withdrawal criteria (Section 6.4).
- Confirm that the subject has not received a dose of systemic antibiotics less than 5 days before blood collection (Section 4.4). If the subject has received such a dose, delay the visit to meet the 5-day exclusionary period.
- Confirm that the subject has not received blood products or immunoglobulin within the last 6 months. If the subject has received such products, discuss delaying the visit with the sponsor.
- Obtain a 5-mL blood sample. Local/topical anesthetic may be applied prior to the blood draw.
- Record any AEs and RRIs occurring within 48 hours after the Visit 12 blood draw as described in Section 8 and the Schedule of Activities.
- Record nonstudy vaccinations received since the last study visit.
- Issue a memory aid.
- Schedule an appointment for the next study visit and confirm that it is scheduled within the time window per protocol.
- Complete the source documents and CRFs.

Final Protocol Amendment 2, 19 April 2016

6.2.3. Visit 13, Study Month 54, Immunogenicity 3 (48 Months After Vaccination 3 ± 30 Days)

- Confirm that the subject continues to be eligible for the study and does not meet any withdrawal criteria (Section 6.4).
- Confirm that the subject has not received a dose of systemic antibiotics less than 5 days before blood collection (Section 4.4). If the subject has received such a dose, delay the visit to meet the 5-day exclusionary period.
- Confirm that the subject has not received blood products or immunoglobulin within the last 6 months. If the subject has received either of these products, discuss delaying the visit with the sponsor.
- Obtain a 5-mL blood sample. Local anesthetic may be applied prior to the blood draw.
- Record any AEs and RRIs occurring within 48 hours after the Visit 13 blood draw as described in Section 8 and the Schedule of Activities.
- Record nonstudy vaccinations received since the last study visit.
- Complete the source documents and CRFs.

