Neisseria meningitidis is a leading cause of bacterial meningitis in infants, adolescents, and young adults in developed countries. In particular, *Neisseria meningitidis* serogroup B (MnB) is responsible for approximately two-thirds of the cases of observed meningococcal infections in Europe, with a case-fatality rate of 6% to 8% from 1999 to 2006. Australian national surveillance data show the peak incidence of disease in children aged 4 years or less, with a secondary peak in adolescents and young adults; approximately 85% of all cases are attributed to serogroup B disease.

A recombinant, multicomponent MnB vaccine (Bexsero) is licensed in Europe, Canada, Australia, Chile, and the United States. Trumenba® (bivalent recombinant lipoprotein 2086 vaccine [bivalent rLP2086]), developed by Pfizer, is approved in the United States for use in individuals 10 through 25 years of age for active immunization to prevent invasive meningococcal disease (IMD) caused by MnB. Recommendations for MnB vaccination are under consideration in various countries. However, to date, no broadly effective vaccine against MnB disease is available worldwide. General availability of a safe and immunogenic MnB vaccine remains an unmet medical need, and a successful vaccine will provide substantial improvement in prevention of meningococcal infection and a reduction in the burden of disease.

Bivalent rLP2086 is targeted to a conserved, surface-exposed lipoprotein, lipoprotein 2086 (LP2086), a meningococcal virulence factor that binds human factor H. *N meningitidis* serogroup B recombinant lipoprotein 2086 (rLP2086) has been expressed in *Escherichia coli* and formulated in a bivalent vaccine composed of 1 subfamily A strain and 1 subfamily B strain of rLP2086.

This study will describe the safety, tolerability, and immunogenicity of bivalent rLP2086 administered at 2 dose levels (60 μ g and 120 μ g) in 2 age strata (12 to <18 and 18 to <24 months old), given in a Month 0, 2, and 6 schedule. The younger age stratum will be substratified into toddlers 12 to <15 and 15 to <18 months of age. Within each age stratum, examination of the 120- μ g dose level will proceed only after the 60- μ g dose level is shown to be safe and tolerable in a sentinel cohort. This study will be conducted in 2 stages:

- Stage 1 includes Visit 1 to Visit 10.

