- e. Chronic conditions and/or medical history of significance, including relevant surgical procedures, allergies (drug/nondrug).
- f. General appearance, skin, head, eyes, nose, ears, throat, heart, lungs, abdomen, extremities, neurologic, musculoskeletal, lymph nodes, height (or length for nonwalking subjects) and weight.
- g. General appearance, ears, throat, heart, and lungs.
- h. Blood must be collected before vaccination and only after eligibility has been confirmed.
- i. Injection performed by unblinded administrator; acute reactions assessed by blinded observer. Location of vaccination should be noted in the source, the CRF and the e-diary.
- j. Between visits, review the e-diary data online at frequent intervals. Contact the parent(s)/legal guardian in order to obtain stop dates for any local reactions, systemic events, or use of antipyretic medication that was ongoing on the last day that the electronic diary (e-diary) was completed.
- k. For additional reporting period details for AEs, SAEs, newly diagnosed chronic medical conditions (NDCMCs) and medically attended events (MAEs), see Section 8.
- 1. Occurring within 48 hours after blood draw.
- m. Checklist includes questions regarding NDCMC and MAEs/AEs.
- n. If required.
- o. An end-of-Stage 1 telephone call will take place after the subject has completed Visit 9 and following sponsor release of randomization codes.

 Abbreviations: AE = adverse event; e-diary = electronic diary; MAE = medically attended event; NDCMC = newly diagnosed chronic medical condition; SAE = serious adverse event.

Schedule of Activities for Stage 2 Duration of MnB-Specific Immune Response (Bivalent rLP2086 Subjects Only)						
Visit Identifier	11	12	13			
Time Period	Month 30	Month 42	Month 54			
Visit Description (Time After Vaccination 3)	Immunogenicity 1 (24 Months)	Immunogenicity 2 (36 Months)	Immunogenicity 3 (48 Months)			
Visit Window	±30 Days	±30 Days	±30 Days			
Confirm continued eligibility	X	X	X			
Obtain 5-mL blood sample	X	X	X			
Record AEs, and, any research-related injury occurring within 48 hours after blood draw	X	X	X			
Record any nonstudy vaccinations	X	X	X			
Issue memory aid	X	X				

Abbreviations: AE = adverse event; bivalent rLP2086 = bivalent recombinant lipoprotein 2086 vaccine; MnB = *Neisseria meningitidis* serogroup B.

TABLE OF CONTENTS

ABBREVIATIONS	3
PROTOCOL SUMMARY	6
LIST OF TABLES	20
1. INTRODUCTION	22
1.1. Mechanism of Action/Indication	22
1.2. Background and Rationale	22

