5.4. Investigational Product Supplies

5.4.1. Dosage Forms and Packaging

The bivalent rLP2086 formulation is described in Table 5 below.

 Table 5.
 Bivalent rLP2086 Investigational Product Formulation

Ingredient	Component Grade	Function	Dose Level	
			60-µg	120-μg
CCI				

B1971035

Final Protocol Amendment 2, 19 April 2016

Table 5. Bivalent rLP2086 Investigational Product Formulation

Ingredient	Component Grade	Function	Dose Level	
			60-µg	120-µg
CCI				

A licensed pediatric HAV vaccine to be administered at Visit 1 (Vaccination 1) and Visit 6 (Vaccination 3) will be provided in a 0.5-mL dose for injection. Information on which licensed pediatric HAV vaccine is to be used is contained in the investigational product manual.

A placebo (sterile saline for injection containing 0.85% sodium chloride in a 0.5-mL dose) will be administered at Visit 4 (Vaccination 2).

The investigational products (bivalent rLP2086 and HAV vaccine/saline) will be provided by the sponsor to each study site. Study vaccines will be packed and labeled as investigational product in accordance with current guidelines and applicable local and legal regulatory requirements. Each investigational product will be labeled with a unique kit number.

HAV vaccine (at Months 0 and 6) has been chosen as the control in this study. In comparison to other recommended vaccines for this age group, HAV vaccine has a better tolerability profile. In addition, HAV vaccine will confer a benefit to subjects who may become at increased risk for hepatitis A viral infection either during future travel or during other exposures. The generally recommended regimen for HAV vaccine is 2 doses at Months 0 and 6. In this study, saline is given at Month 2 to maintain the study blind.

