5.4.3. Administration

Standard vaccination practices must be observed and vaccine must not be injected into blood vessels. Appropriate medication and other supportive measures for management of an acute hypersensitivity reaction should be available in accordance with local guidelines for standard immunization practices.

Administration of investigational products should be performed by an appropriately qualified, Good Clinical Practice (GCP)-trained, and vaccine-experienced member of the study staff (eg, physician, nurse, physician's assistant, practitioner, pharmacist, or medical assistant) as allowed by local, state, and institutional guidance. In this observer-blinded study, the study staff dispensing and administering the vaccine will be unblinded, but all other site personnel, including the principal investigator (PI), will be blinded.

Only a third-party unblinded medically qualified member of the study staff will administer the investigational product. Investigational product administration details (ie, date of administration, kit number, volume, route, and site of administration) will be recorded on the CRF. Investigational product accountability will be documented as per Section 5.6.

As shown in Table 6, bivalent rLP2086 will be administered 3 times over the course of the study: the first vaccination at Visit 1 (Month 0), second vaccination at Visit 4 (Month 2), and third vaccination at Visit 6 (Month 6). Bivalent rLP2086 will be administered as an intramuscular injection into either the deltoid muscle or anterolateral thigh muscle. If muscle mass in the deltoid is not adequate for intramuscular injection, then the thigh is the preferred injection site. Site of administration (eg, left/right arm/thigh) should be noted in the source notes and the CRF.

HAV vaccine will be administered twice over the course of the study: the first vaccination at Visit 1 (Month 0) and third vaccination at Visit 6 (Month 6). Saline will be administered at the second vaccination (Month 2) time point. HAV vaccine/saline will be administered as an intramuscular injection into either the deltoid muscle or anterolateral thigh muscle. If muscle mass in the deltoid is not adequate for intramuscular injection, then the thigh is the preferred injection site. Site of administration (eg, left/right arm/thigh) should be noted in the source notes and the CRF.

The schedule of vaccine administration is shown in Table 6 and the Schedule of Activities.

B1971035

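### Section 6.1.12 sends some fully dosed controls for another HAV dose, and Section 6.1.11 cites the wrong telephone call for discontinued sentinel subjects

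*Protocol*

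**What the plan says.** **HAV advice.** Protocol Section 6.1.12 describes a call about 6 months after the last study vaccination for subjects who withdraw before Visit 8. Its last instruction is that the parents of any child assigned to HAV vaccine/saline "who did not complete Stage 1 should be informed to make arrangements to have the subject receive a booster vaccination of HAV vaccine". It sets no condition on how many HAV doses the child has had. The Protocol Summary states that "Stage 1 includes Visit 1 to Visit 10". Section 5.4.1 states that "The generally recommended regimen for HAV vaccine is 2 doses at Months 0 and 6", and Section 5.4.3 gives controls HAV vaccine at Visits 1 and 6, with saline in between. For those who reach the end, Section 6.1.10 says: "All subjects randomly assigned to HAV vaccine who complete Stage 1 will finish the study requirements with this contact".

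**Safety call.** Under Section 6.1.11, the family of a discontinued sentinel subject is told that "a telephone contact (Section 6.1.10) will occur approximately 6 months following the last study vaccination for safety follow-up". Section 6.1.10 is the Visit 10 contact. Footnote o of the Stage 1 Schedule of Activities places it late: "An end-of-Stage 1 telephone call will take place after the subject has completed Visit 9 and following sponsor release of randomization codes". Section 6.1.10 itself adds: "Only when the randomization codes have been released by the sponsor/designee to the investigator may Visit 10 occur".

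**The concern.** The first instruction depends on whether the child completed Stage 1, when what matters is whether the child has completed the HAV schedule. The two differ for a control who withdraws after the Visit 6 dose.

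The second sends a 6-month safety call to a section written for children who have finished Stage 1. A site that follows the citation literally finds no AE questions. It also finds no notice for a control who has had one HAV dose and is owed another.

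What is at stake is participant care. Benefit to the control child is a stated reason for choosing HAV vaccine (Sections 3.1 and 5.4.1), and children stopped on committee advice should have an unambiguous follow-up call. No sample size, analysis population or statistical method depends on either passage.

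**Working it through.** The plan states no figure to reproduce. The check is a dose count, a timing comparison and a comparison of the two calls.

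**1. Does the Stage 1 condition select anyone?** Section 6.1.12 covers withdrawal before Visit 8, and Stage 1 ends at Visit 10. Everyone in the section is therefore a Stage 1 non-completer, and the condition excludes no one.

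**2. HAV doses for a control in Section 6.1.12** (study doses only)

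| Time of withdrawal | Study doses | Advised | Total | Stated schedule |
|---|---|---|---|---|
| After Visit 1, before the Visit 6 dose | 1 | 1 | 2 | 2 |
| After the Visit 6 dose, before Visit 8 | 2 | 1 | 3 | 2 |

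The advice is right in the first row and one dose too many in the second. The second row spans the 168 to 196 days between Visit 6 and Visit 8. The documents give no withdrawal rate for that interval, and none is assumed here.

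**3. Could a third dose be intended?** The visit windows put Visit 6 at 42 + 105 = 147 to 70 + 126 = 196 days after Visit 1, so some controls have their two doses less than 6 months apart. But a control with the same two doses who completes Stage 1 gets no such advice under Section 6.1.10. The documents therefore do not treat two study doses as insufficient.

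**4. Timing of the call cited in Section 6.1.11**
- The Visit 10 call follows Visit 9. The earliest in-window Visit 9 is 42 (Visit 4) + 105 (Visit 6) + 337 (Visit 9) = 484 days after Visit 1.
- The Section 6.1.11 call is due about 6 months after the last vaccination. Taking 6 months as about 183 days (365/2 = 182.5), that is about day 183 after one dose. After a second dose at days 42 to 70 it is 42 + 183 = 225 to 70 + 183 = 253.
- Visit 9 is dated from Visit 6, so a child stopped before Vaccination 3 has no Visit 9 at all.

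**5. Content of the two calls**

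| Item | 6.1.10 | 6.1.12 |
|---|---|---|
| About 6 months after last vaccination | No | Yes |
| AE checklist, chronic-condition and neuroinflammatory inquiry | No | Yes |
| Nonstudy vaccinations recorded | Yes | Yes |
| Instructions for Stage 1 non-completers | No | Yes |
| HAV notice | No | Yes |

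Section 6.1.12 matches the call that Section 6.1.11 describes, and Section 6.1.10 does not.

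**6. How many children the citation can affect.** Each sentinel cohort has about 33 children, randomized 2:1, so 33 × 1/3 = 11 controls. Under Section 3.2.1, unacceptable 60-µg data in the older cohort halt both 60-µg cohorts: 2 × 33 = 66 children, of whom 2 × 11 = 22 are controls. These are upper bounds. A stopping rule can pause enrollment before a cohort fills (Section 7.9), and Section 6.1.11 also covers single subjects.

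**The case against.** On the HAV advice, a site may read a booster as the outstanding second dose of a 2-dose course and check the administration dates. That is a sensible reading, and some sites would adopt it. It stands as mitigation only, because the text does not ask for the check.

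On the safety call, the objection is stronger. Section 6.1.12 opens with all subjects who withdraw before Visit 8 and does not exclude sentinel subjects. Section 6.1.4 describes sentinel subjects stopped on committee advice as withdrawn from the study. Section 6.1.12 therefore arguably covers them already. The choice between 6.1.11 and 6.1.12 in Section 6.4 need not be exclusive, since one is a clinic visit and the other a later call. Section 8.3 keeps serious AE reporting active for 6 months after the last dose, and Section 8.13 requires parents to be questioned about AEs. Section 6.1.11 itself states the call's safety purpose.

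Most of this stands. A reader might infer that 6-month safety data from discontinued sentinel subjects would be lost, and the documents do not support that. What remains is that Section 6.1.11 points only to 6.1.10, so sites could conduct the call differently, and a one-dose control could miss the HAV notice. Sections 8.3 and 8.13 do not supply that notice.

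**Conclusion.** Both instructions are wrong as written, and both are minor.

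- **HAV advice:** the error is confined to controls who withdraw after the Visit 6 dose and before Visit 8. A reader might infer that fully dosed controls in general are sent for a third dose; those who complete Stage 1 are not. A reader might also infer harm from an extra dose; the documents say nothing to that effect.
- **Safety call:** the citation has no effect if no sentinel subject or cohort is discontinued. Otherwise the ceiling is the 33 children per cohort, or 66 for both 60-µg cohorts, derived above. The consequence is a possible inconsistency in the call and a possible missed notice.

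The conclusion rests on the protocol text. The study reference manual, to which these sections defer for some details, was not available and may already clarify either point.

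**What to change.** 1. In Section 6.1.12, replace the Stage 1 condition with: *who has not completed the 2-dose HAV schedule according to the HAV doses recorded in the CRF*. The sponsor's clinicians should say whether a nonstudy HAV dose counts, since Section 5.7.1 requires withdrawal of a child who receives one during Stage 1.
2. In Section 6.1.11, change the cited section from 6.1.10 to 6.1.12.
3. In the same amendment, confirm how the site obtains the allocation for these calls. Section 5.2.1.2 times code release after Visit 8, while Section 6.1.12 already has the site disclose the group to every early withdrawal about 6 months after the last dose. The AE inquiry does not depend on the allocation.

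The cost is one phrase, one section number and one sentence of confirmation at the next amendment. No new data are needed: administration details are already on the CRF (Section 5.4.3), and Sections 6.1.11 and 6.1.12 already record nonstudy vaccinations.
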